3.8.2.9 Patient reported outcomes

The European Organisation for Research and Treatment of Cancer's core quality of life questionnaire (EORTC-QLQ-C30, version 3.0) [REDACTED]

[REDACTED] will be used to evaluate patient-reported outcome measures of health-related quality-of-life, [REDACTED]

The PRO instruments are planned to be administered during screening and every 8 weeks after randomization in the first 18 months, and every 12 weeks thereafter (including at EOT) until disease progression, death, withdrawal of consent, loss to follow-up or subject/guardian decision.

The following time based intervals will be used to group the PRO data over time. Day is defined as date of PRO assessment date – randomization date + 1.

Table 3-6 Time windows for patient reported outcomes

Assessment	Time Interval
Baseline	Screening assessment
Cycle 3, 5, 7, 9 until cycle 19	+/- 4 weeks centered around the planned assessment date (except for the first window and the last window): i.e. days (1, 85] for Day 1 of cycle 3 (2 nd assessment) days (85, 141] for Day 1 of cycle 5 (3 rd assessment) days (k*56-27; k*56+29] for (k+1 th assessment) days (477, 547] for 10 th assessment on Day 1 cycle 19
Cycle 22, 25, 28, ...	+/- 6 weeks centered around the planned assessment date: i.e. days (547, 631] for 11 th assessment days (631, 715] for 12 th assessment days (715, 799] for 13 th assessment

If more than one assessment is done within the same time window, the assessment performed closest to the target date will be used. If 2 assessments within a time window are equidistant from the target date, then the assessment obtained prior to target date will be used.

The global health status/QoL scale score of the EORTC QLQ-C30 is identified as a primary PRO variable of interest. The physical functioning, emotional functioning and social functioning sub-scale scores of the EORTC QLQ-C30, [REDACTED]

[REDACTED] are identified as secondary PRO variables of interest.

The number of patients completing PRO questionnaires and the number of patients missing/expected to have PRO assessments will be summarized by treatment arm for scheduled assessment time points (the number of ongoing patients will be used as denominator). Furthermore, the amount and the pattern of missing data may be explored by treatment arm and over time using summary statistics. The following categories will be used to describe whether the questionnaire was completed at a specific time point:

- yes, fully completed
- yes, partly completed
- no.

Scoring of raw data and methods for handling missing items or missing assessments will be handled according to scoring manuals for each respective patient questionnaire ([Fayers 2001](#); [Oemar and Janssen 2013](#); [Cleeland 2009](#)).

Descriptive statistics (n, mean, median, SD, min, max) will be used to summarize the [REDACTED] scores from the EORTC QLQ-C30 [REDACTED]

[REDACTED] at each scheduled assessment time point. Additionally, change from baseline in the [REDACTED] scores at the time of each assessment will be summarized. [REDACTED]

[REDACTED] Patients with an evaluable baseline score and at least one evaluable post baseline score during the treatment period will be included in the change from baseline analyses.

A repeated measures model for longitudinal data will be used to compare the two treatment arms in sub-scales obtained from EORTC QLQ-C30 [REDACTED] over time. This longitudinal model will include terms for treatment, the randomization stratification factors (presence of lung and/or liver metastases [yes versus no] and previous treatment with any CDK4/6 inhibitor [yes versus no]), time (duration in weeks counting from the time of baseline measurement to the time of a particular post baseline measurement) and baseline value as main effects, as well as an interaction term for treatment by time. Time will be explored as both a continuous and categorical variable to assess the best model fit. As a first approach, an unstructured correlation matrix will be used to model the correlation within patients. The structure of the correlation matrix will be investigated and simplified using likelihood ratio tests if appropriate. The differences in least square means between treatment and control group, and the corresponding 2-sided 95% CI at selected time points will be presented. Data collected under treatment (i.e. while the patient is treated) and during post-treatment follow-up up until documented progression will be included. If the model fit based on unblinded data does not achieve convergence then fewer time points for inclusion may be considered.

[figure not shown]
Time to 10% deterioration in the global health status/ [REDACTED] will be assessed in each cohort. 10% deterioration is defined as a worsening in score by at least 10% compared to baseline, with no later improvement above this threshold observed during the treatment period, or death due to any cause. Time to deterioration is the number of days between the date of randomization and the date of the assessment at which deterioration is seen. If a patient has not had an event prior to analysis cut-off, start of new anti-neoplastic therapy, lost to follow-up, or withdrawal of

consent, the time to deterioration will be censored at the date of the last evaluation before the earliest of these dates. If deterioration is observed after two or more missing assessments, time to deterioration will be censored at the date of the last assessment prior to the deterioration. Patients with no baseline data will be censored at Day 1. Death is considered as an event when it occurs within a period of time defined by 2 times the period between two assessments as planned in the study protocol. This avoids overestimating the time to definitive worsening in patients dying after an irregular assessment scheme. Patients who die after more than twice the planned period between two assessments since the last assessment are censored at the date of their last available questionnaire.

Time to 10% deterioration will be compared between the two treatment arms using a stratified log-rank test (strata based on IRT data) and the survival distributions will be presented descriptively using Kaplan-Meier curves. Summary statistics from the Kaplan-Meier distributions will be determined, including the median time to 10% deterioration and the proportions of patients without 10% deterioration at 6, 12, 18 months. Both point estimates and 95% CIs will be presented. A stratified Cox regression model will be used to estimate the hazard ratio (HR) of time to deterioration, along with 95% confidence interval. Sensitivity analysis of time to definitive deterioration with different cut-off definitions (e.g. 5%, 15%) may also be considered if the number of events per arm is judged sufficient to draw relevant conclusions.

The figure consists of a series of horizontal black bars of varying lengths and positions on a white background. The bars are arranged in a descending order of length from top to bottom. The first few bars are very long, while the last few are very short. The bars are positioned at different horizontal locations, with some being centered and others shifted to the left or right. The overall pattern suggests a sequence of data points or events, possibly representing a signal or a series of measurements.

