6.3.2.1.2 Guidelines for the treatment of study drug induced skin toxicity

Skin toxicity is a class-effect adverse event observed with PI3Ki/mTORi agents.

Close monitoring of potential skin reactions will be performed at each planned visit and will be reported as adverse event. The most frequent skin adverse events reported are: maculopapular rash (only a minority present acneiform rash); pruritus and dry skin. The onset is typically within the first 2 months of treatment start and is reversible with adequate comedication and treatment interruption if needed. Skin reactions may improve over several weeks. Consultation with a dermatologist is highly recommended for better assessment and management of alpelisib-induced skin toxicity at any grade, and mandated if severe cutaneous reaction like

Stevens-Johnson-Syndrome, Toxic Epidermal Necrolysis or Erythema multiforme or Drug Reaction with Eosinophilia and Systemic Symptoms (DRESS) is suspected. Workup for skin toxicity events includes skin photography, a complete blood count with differential, and a full chemistry panel. A paired skin biopsy should be obtained (from both affected and an unaffected skin area) for local histopathology assessment to further assess the skin toxicity, especially to confirm suspected diagnosis of any severe cutaneous reactions.

Skin photographs must be taken and skin biopsy must be performed in case of Grade 4 skin toxicity and any grade of suspected severe cutaneous reactions. In case of Grade 3 skin toxicity, Novartis recommends that photographs are taken and a skin biopsy is performed.

Skin biopsy will be sent to a Novartis designated laboratory, together with dermatologist and pathologist reports, if available, for further research purpose on the pathology and mechanism of PI3K inhibitor treatment induced skin toxicity

Antihistamines administered prior to rash onset may decrease incidence and severity of rash based on Study CBYL719C2301; therefore, at the Investigator's discretion, non-sedating antihistamines (e.g. cetirizine (Zyrtec[®]), fexofenadine (Allegra), loratadine (Claritin)) may be used as prophylactic treatment to reduce severity of rash in all patients and especially for patients with a history of atopy such as allergic rhinitis, asthma, atopic dermatitis, or drug allergies.

For any grade of severe cutaneous reactions, alpelisib treatment must be permanently discontinued without any re-challenge.

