7.1.6 Efficacy follow-up

If a patient did not discontinue study treatment due to documented disease progression, death, lost to follow-up, or withdrawal of consent for efficacy follow-up, tumor and PRO assessments should continue to be performed every 8 weeks during the first 18 month and then every 12 weeks until 36 months, then change to as clinically indicated until documented disease progression, death, lost to follow-up, or withdrawn consent to efficacy follow-up. At that time, the reason for study completion should be recorded on the Study Phase Completion Disposition CRF page. All tumor evaluation images collected during the efficacy follow-up phase will be sent to central vendor for independent review.

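### In time to 10% QoL deterioration, a worsening can be cancelled only by recovery during treatment, so patients who stop both study drugs and then recover in PRO follow-up stay counted as events

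*SAP*

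**What the plan says.** SAP 3.8.2.9 sets the event in two parts. First, the size: "10% deterioration is defined as a worsening in score by at least 10% compared to baseline". Second, persistence: the worsening must stand "with no later improvement above this threshold observed during the treatment period, or death due to any cause". A patient is censored at the last evaluation if there is no event "prior to analysis cut-off, start of new anti-neoplastic therapy, lost to follow-up, or withdrawal of" consent. End of study treatment is not on that list.

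The same section has the questionnaires given "until disease progression, death, withdrawal of consent, loss to follow-up or subject/guardian decision". Protocol 7.1.6 says that, for patients who stop treatment for other reasons than progression, death, loss to follow-up or withdrawal of consent, "tumor and PRO assessments should continue to be performed every 8 weeks during the first 18 month" and every 12 weeks after that. Protocol Table 7-10 repeats this for efficacy follow-up.

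For the repeated-measures model, also in SAP 3.8.2.9, the scope is wider: "Data collected under treatment (i.e. while the patient is treated) and during post-treatment follow-up up until documented progression will be included".

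Time to 10% deterioration in this scale is a listed secondary endpoint (Protocol Table 3-1, SAP Table 1-1). The SAP plans a stratified log-rank test, Kaplan-Meier estimates and a stratified Cox hazard ratio for it.

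**The concern.** A persistence rule is there to separate lasting loss of quality of life from a passing dip. Here the dip may be recorded at any PRO assessment, on or off treatment, while the recovery counts only if it is recorded on treatment. A patient who comes off both drugs because of toxicity, is below the threshold at the end-of-treatment visit, and is back above it at the next follow-up questionnaire is coded as deteriorated. She may be progression-free and on no new therapy at that point.

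The protocol describes some alpelisib toxicity in terms that make such recovery likely. Skin toxicity, for example, "is reversible with adequate comedication and treatment interruption if needed" (Protocol 6.3.2.1.2). At stake is the interpretation of the hazard ratio for the main PRO endpoint. Type I error for PFS and OS is not touched.

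**Working it through.** The documents give no event count, power or error rate for this endpoint, so there is no stated figure to reproduce. The check sets the rules side by side and then runs two hypothetical patients through them.

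**Which scores the rules use**

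| Rule | Where | Scores that count |
|---|---|---|
| Worsening that creates an event | SAP 3.8.2.9 | Any, up to cut-off, new therapy, loss to follow-up or withdrawal of consent |
| Improvement that cancels it | SAP 3.8.2.9 | Treatment period only |
| Repeated-measures model | SAP 3.8.2.9 | On treatment and in follow-up, to progression |
| Definitive 10% deterioration | Protocol 10.5.4 | No cancellation rule and no treatment-period limit |
| ECOG definitive deterioration | SAP 3.8.2.8 | Any later improvement cancels |
| ECOG definitive deterioration | Protocol 10.5.2.6 | Later improvement in the treatment period cancels |

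The model's wording separates time under treatment from post-treatment follow-up, so the treatment period cannot readily be read to include that follow-up. The protocol's ECOG rule carries a similar limit, but ECOG status is last assessed at the end-of-treatment visit (Protocol 7.2.2.4), so it has little effect there. For PROs, where collection continues, the limit does have an effect.

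**Patient A (hypothetical): worsens on treatment, recovers off it**
- Baseline 66.7, so the threshold is 0.9 × 66.7 = 60.0.
- Week 8: 50.0, a fall of 16.7/66.7 = 25%. Both study drugs are then stopped, and the score at the end-of-treatment visit is still below 60.0.
- Week 16, in follow-up: 75.0, with no progression and no new therapy.
- As written (recovery taken to lie outside the treatment period): event at week 8. If any later score could cancel: no event, and the patient stays at risk.

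**Patient B (hypothetical): worsens and recovers, both off treatment**
- Same baseline. Both drugs are stopped while the score is above 60.0; it is 50.0 at one follow-up assessment and 75.0 at the next.
- As written: event. With a symmetric rule: no event. Here the scores come from the same phase of follow-up, and only the unfavourable one is used.

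**Who is exposed**
- Protocol 6.1.2, 6.3.1.2 and 7.1.3 let a patient who stops one drug continue the other on the same assessments. Protocol 7.1.3 ties the end-of-treatment visit to stopping both.
- SAP 2.1.5 dates the last study treatment by the last non-zero dose of either component.
- A patient who stops alpelisib/placebo alone is therefore still in treatment, and her recovery does cancel.

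**Effect of a possible 30-day window**
- SAP 2.1.9 uses last dose + 30 days for safety. Suppose it applied here, and that stop dates are spread evenly over the interval between scheduled PROs (assumption, ignoring visit windows).
- 8-weekly phase: 30/56 = 54% of first post-stop scheduled scores would fall inside.
- 12-weekly phase: 30/84 = 36%.
- Later scheduled follow-up scores would be at least one full interval (56 or 84 days) further on, and so outside.

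**The case against.** **Toxicity stops are mostly stops of alpelisib/placebo alone.** Table 6-3 is largely written that way, and such patients may remain on fulvestrant. This stands, and it limits the point to patients who stop both drugs. A reader might infer that anyone who stops alpelisib for toxicity is caught by the rule; the documents do not support that.

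**The size is unknown.** A reader might take the phase I figures in Protocol 1.2.3.3 (AEs leading to drug discontinuation in 0% of patients at 300 mg and 13% at 400 mg) and apply them to about 170 mutant-cohort patients on alpelisib, reaching 0.13 × 170 = 22 exposed. That does not hold. The 13% belongs to a dose not used as the starting dose here, the 300 mg group in Table 1-2 has 9 patients, and the text does not say that fulvestrant was stopped too. Any count of wrongly coded events built on that figure would also need assumed rates of worsening and recovery.

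**The protocol is stricter still.** Read literally, Protocol 10.5.4 has no cancellation rule, so Patient A is an event there as well. True, but the protocol calls the deterioration definitive without defining the word. Once the SAP admits recovery as grounds for cancelling, it needs a reason for ignoring part of the recovery data.

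**Post-stop recovery is visible elsewhere.** The repeated-measures model includes it, and two analyses may have different scopes. That is fair, but it does not correct this hazard ratio.

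**Low stakes.** Protocol 10.5.4 foresees no formal PRO tests and no multiplicity adjustment, and any bias would probably run against alpelisib, so it would not manufacture a benefit. This stands as a limit on importance.

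**Conclusion.** The asymmetry is real on the plain wording. For patients who stop both study drugs without progression or new anti-neoplastic therapy, a recovery in PRO follow-up cannot cancel a worsening, at least once any 30-day on-treatment window has passed. Whether such a window applies is undefined for this endpoint.

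The direction of bias is conditional. If stops of both drugs are more frequent with alpelisib, the hazard ratio is biased against alpelisib. That is plausible, since fulvestrant is common to both arms, but the documents do not show it. A reader might infer a material, one-sided distortion; neither the number of patients nor the shift in the hazard ratio can be derived, so that reading goes too far. The consequence is confined to a secondary endpoint outside the alpha-controlled testing.

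**What to change.** In SAP 3.8.2.9, replace the restriction to the treatment period with: *observed at any later PRO assessment up to documented progression, start of new anti-neoplastic therapy or cut-off*. This brings post-treatment scores up to progression into the rule, as in the repeated-measures model.

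Keep the on-treatment version as a sensitivity analysis. Define its treatment period, stating whether it ends at the last dose of either drug, at the end-of-treatment visit or 30 days after the last dose.

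The cost is one sentence, one definition, a small change to the derivation and one extra run. No new data are needed, because the follow-up questionnaires are already scheduled.

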3.9 Safety evaluation

The assessment of safety will be based mainly on the frequency of adverse events and on the number of laboratory/ECG values that fall outside of pre-determined ranges. Other safety data (e.g. vital signs and special tests) will be considered as appropriate.

All safety outputs will use the safety set and be presented by treatment arm for the *PIK3CA* mutant and non-mutant cohorts individually as well as combined. The safety summary tables will include only 'on-treatment' events/assessments, i.e. those collected on or after the first date of study treatment and collected no later than 30 days after the date of last study treatment administration. The AEs started before the first dose but worsening during the treatment period are also considered as 'on-treatment' events. All safety events/assessments will be listed and those collected outside of the on-treatment window will be flagged.

3.9.1 Adverse events (AEs)

3.9.1.1 Coding of AEs

Adverse events are coded using the Medical Dictionary for Regulatory Activities (MedDRA) terminology.

3.9.1.2 Grading of AEs

AEs will be assessed according to the Common Terminology Criteria for Adverse Events (CTCAE) version 4.0.3.

The CTCAE represents a comprehensive grading system for reporting the acute and late effects of cancer treatments. CTCAE v4.0.3 grading is by definition a 5-point scale generally corresponding to mild, moderate, severe, life threatening, and death.

If CTCAE grading does not exist for an adverse event, grades 1 – 4 corresponding to the severity of mild, moderate, severe, and life-threatening will be used. CTCAE grade 5 (death) will not be used in this project; if an AE results in death it will be documented in the outcome ("fatal"). Information on deaths will also be collected on the 'Death' CRF.

3.9.1.3 General rules for AE Reporting

AE summaries will include all AEs starting on or after study Day 1 (i.e. on or after the day of the first intake of study treatment) and starting no later than 30 days after the last administration

of study treatment (see [Section 2.1.5](#)). All AEs will be listed. AEs starting prior to study Day 1 and AEs starting later than 30 days after the last treatment date will be flagged in the listings.

AEs will be summarized by presenting the number and percentage of patients having at least one AE, having at least one AE in each system organ class, and for each preferred term using MedDRA coding. A subject with multiple occurrences of an AE will be counted only once in the AE category.

Separate AE summaries will be presented by system organ class, preferred term, and maximum CTC grade. A patient with multiple CTC grades for an AE will be summarized under the maximum CTC grade recorded for the event. In the summaries presented by grade, all AEs will be pooled regardless of whether they are CTC gradable or not. AE with missing CTCAE grade will be included in the 'All grades' column of the summary tables.

The frequency of CTC grade 3 and 4 AEs will be summarized separately.

Any information collected (e.g. CTC grades, relationship to study treatment, action taken etc.) will be summarized and listed as appropriate.

3.9.1.4 AE summaries

The following adverse event summaries will be produced:

- AEs by SOC, PT, maximum CTCAE grade
- Most frequent AEs, regardless of study treatment relationship by PT, maximum CTCAE grade (*at least 5% incidence*)
- Treatment-related AEs by SOC, PT, maximum CTCAE grade
- Most frequent treatment-related AEs by PT, maximum CTCAE grade (*at least 5% incidence*)
- On-treatment deaths by primary SOC and PT
- On-treatment deaths and SAEs with fatal outcome by PT
- All deaths by SOC, PT. (*All deaths (on-treatment + post treatment) are included*)
- Serious adverse events by SOC, PT, maximum CTCAE grade
- Treatment-related serious adverse events by SOC, PT, maximum CTCAE grade
- Most frequent SAEs by PT and maximum CTCAE grade
- Most frequent treatment-related SAEs by PT and maximum CTCAE grade
- AEs leading to study drug discontinuation by SOC, PT and maximum CTCAE grade
- Treatment-related AEs leading to study drug discontinuation by SOC, PT and maximum CTCAE grade
- AEs requiring dose adjustment and/or interruption by SOC, PT, maximum CTCAE grade.
- AEs requiring medication or therapies by SOC, PT, maximum CTCAE grade.

AEs of special interest will also be summarized. See [Section 3.9.1.5](#) for the grouping details.

3.9.1.5 Adverse Events of Special Interest

Specific groupings of Adverse Events of Special Interest (AESI) will be considered and the number of patients with at least one event in each grouping will be reported. Such groups consist of AEs for which there is a specific clinical interest in connection with alpelisib treatment (i.e. where alpelisib may influence a common mechanism of action responsible for triggering them) or AEs which are similar in nature (although not identical). The groups are defined according to the MedDRA terms defined in the program Case Retrieval Strategy (CRS) document and will be summarized. The latest version of the CRS document available at the time of the analyses will be used.

All AESI groupings are defined through the use of Preferred Terms (PT), High Level Terms (HLT) or System Organ Classes (SOC) or through a combination of these three components. An Excel file with the exact composition of the AEs groupings is to be used to map reported AEs to the AESI groupings. This file may be updated (i.e. it is a living document) based on review of accumulating trial data. Note that certain AEs may be reported within multiple groupings. Final deliverables will be aligned with the final excel file. A listing of all grouping levels down to the MedDRA preferred terms used to define each AESI will be generated.

Groupings for Adverse Events of Special Interest

AESI grouping*	Definition*
Hyperglycemia	SMQ Hyperglycaemia /new onset diabetes mellitus (narrow)
Rash	NMQ Rash (BYL719)
Pneumonitis	SMQ Interstitial lung disease (narrow)
GI Toxicity Nausea, Vomiting, Diarrhea	HLT Diarrhoea (excl infective) HLT Nausea and Vomiting symptoms

* At the time of the analyses, MedDRA-defined (SMQ) or Novartis-defined (NMQ) groupings for all identified and potential risks as described in the latest version of the CRS document available will be used

Standard data of analysis for AESI will be conducted as follows:

- The number (%) of patients with AESI will be reported by AESI grouping, maximum CTCAE grade and by treatment group.
- All AEs of special interest will be listed.
- Depending on the observed number of events, the time to first occurrence of any CTC grade ≥ 2 AESI may be summarized using Kaplan-Meier methods for each of the groupings in the table above. Median time to onset and 95% CI will be summarized. Ascending Kaplan-Meier plots will be generated. Please refer to [Section 3.9.1.5.1](#) for definitions. For the AESI of 'Hyperglycemia', 'Rash' and 'GI Toxicity Nausea, vomiting and Diarrhea', additional analyses for time to first occurrence of any CTC grade ≥ 3 AESI will be presented.

